3 OBJECTIVES

The objective of this Sample Size Re-estimation is to provide the sizes of the PPS and FAS which, given the observed variability at this point in time, will guarantee approximately 90% power to detect a dose response relationship and provide sufficient precision in the estimation of the dose response curve and of doses that will be selected for the Phase 3 program of ACT-132577.

4 CHANGES OR CLARIFICATIONS TO ANALYSES PLANNED IN THE STUDY PROTOCOL

Not applicable.

5 DEFINITIONS OF VARIABLES

Baseline refers to the last non-missing value before double-blind treatment start date.

5.1 Screening failures

Not applicable.

5.2 Subject characteristics

Not applicable.

5.3 Study treatment exposure and compliance

Not applicable.

5.4 Study discontinuation

Not applicable.

5.5 Efficacy variables

5.5.1 Primary efficacy endpoint(s)

The primary efficacy endpoint is the change from baseline to Week 8 of double-blind treatment period (Period II) in mean trough (i.e., 24 hours post-dose) SiDBP, measured by OBPM.

Here, baseline is defined as in Section 5 and Week 8 is the time window of Visit 7 [Section 11.1]. OBPM SiDBP is measured by BpTRU[®] (automated; average over five measurements) and is collected via electronic data transfer from an external [REDACTED]. It will not be (re-)calculated by the sponsor.

All assessments (including the unscheduled ones) are considered and re-assigned to the most appropriate visit according to the time windows described in Section 11.1.

5.5.2 Secondary efficacy endpoint

Of the secondary efficacy endpoints defined in the protocol, the following is considered as supportive for the sample size re-estimation:

- Change from baseline to Week 8 of double-blind treatment period (Period II) in mean trough SiSBP, measured by OBPM.

Here, baseline is defined as in Section 5 and Week 8 is the time window of Visit 7 [Section 11.1]. OBPM SiSBP is collected via electronic data transfer and will not be (re-)calculated by the sponsor.

All assessments (including the unscheduled ones) are considered and re-assigned to the most appropriate visit according to the time windows described in Section 11.1.

5.6 Safety variables

Not applicable.

6 DEFINITION OF PROTOCOL DEVIATIONS

For the purpose of this SSR only two major protocol deviations (PDs) will be considered in the definition of the PPS [see Section 7.1.3].

- Not completing the double-blind treatment period: no Week 8 (i.e., time window Visit 7) efficacy data available.
- Use of forbidden medication, indicated as protocol deviation (PD code list version 2, PV_MM.503).

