6 DEFINITION OF PROTOCOL DEVIATIONS

PDs include deviations from inclusion and/or exclusion criteria and deviations from the protocol during the conduct of the study, classified as per latest version of PD code list. Each PD is reported in the SDTM DV domain and categorized according to time period:

1. PD at Screening
2. PD during Run-in period
3. PD at Visit 4 / Pre-randomization

4. PD during DB treatment period
5. PD during withdrawal period and follow-up

Each PD is classified as important or not. Only important PDs during time periods 3, 4 and 5 will be summarized by treatment group for the RND set. (All PDs will be listed.)

Note that an important PD does not necessarily lead to exclusion from the PPS [see Section 7.1.6], whereas an unimportant PD may lead to exclusion from the PPS. The subset of PDs *leading to exclusion* from the PPS are:

1. Double-blind treatment duration less than 49 days: PV_PP.535.
2. No or no valid Week 8 SiDBP (hence, no primary endpoint): PV_PP.501 and PV_MM.501.
3. Anti-hypertensive treatment still ongoing at randomization: PV_MM.307.
4. Taking medication during the double-blind treatment interfering with the primary efficacy parameter (SiDBP): PV_MM.503, PV_MM.504, PV_MM.506, PV_MM.507, PV_MM.508, PV_MM.509, PV_MM.534.
5. Compliance with double-blind treatment < 80% or > 120% or treatment not taken as per protocol: PV_PP.502 and PV_MM.515.

Note that exclusion will be done on a subject basis (rather than on subject / visit basis). In this particular study this approach is not unreasonable since PDs 1–5 are related to the 8 week DB treatment period and the primary efficacy endpoint is measured at the end of that period.

The one PD *leading to exclusion* from the Pharmacokinetic (PK) Set [see Section 7.1.6] is that the PK sample for that subject/visit was not taken at trough: PV_MM.512.

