*Expected number. Power based on the MCT test in the MCP-Mod procedure as implemented in the R DoseFinding package, averaged over the four dose-response curves in Figure 2 of this protocol.
 MCP-Mod = Multiple Comparison Procedure - Modeling; MCT = Multiple Contrast Test; PPS = Per-Protocol Set; SD = standard deviation.

Here, SD is the standard deviation of the primary endpoint (independent of treatment assignment, as this is blinded). It is acknowledged that this could be an overestimation of the (unobserved) within group SD, but, given the range of anticipated treatment group differences, this overestimation is likely to be small (< 5%; simulation program in [Appendix 15.2](#)). The re-calculated size of the PPS is expected to be between 280 subjects and the originally foreseen 420 subjects.

The associated number of subjects to be randomized will be calculated by dividing PPS size by the proportion of randomized subjects who were included in the PPS. That proportion will be estimated based on the same 100 randomized subjects considered for the blinded sample size re-estimation. To be conservative, the lower limit of the 95% CI around the proportion will be employed, of which some examples are given in [Table 3](#).

Table 3 **Number and proportion of subjects in PPS and 95% CIs for the proportion at the time of the sample size re-estimation**

Number Randomized	Number in PPS	Proportion in PPS	95% CI*	
100	95	0.95	0.89	0.98
100	90	0.90	0.82	0.95
100	85	0.85	0.76	0.91
100	80	0.80	0.71	0.87

*Clopper-Pearson [[Clopper 1934](#)]

The number of subjects to be randomized will also take into account the need to collect sufficient exposure and safety data and is expected to be between 300 subjects and the originally planned 540 subjects.
CI = confidence interval; PPS = Per-Protocol Set.

The re-calculated number of subjects randomized is expected to be between 300 subjects and the originally foreseen 540 subjects.

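### The re-estimation measures the per-protocol share with fewer exclusions than the final analysis applies, so the share behind the number randomized is biased upward

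*SAP*

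**What the plan says.** Protocol 11.5.3 takes both the SD and the PPS share from the PPS among the first 100 randomized subjects. Protocol 11.1.3 defines that set as FAS subjects with a Week 8 SiDBP and no major deviation, and leaves the list of deviations to the SAP.

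The re-estimation SAP, Section 6, uses a shorter definition: "For the purpose of this SSR only two major protocol deviations (PDs) will be considered in the definition of the PPS". The first is "Not completing the double-blind treatment period: no Week 8 (i.e., time window Visit 7) efficacy data available". The second is forbidden medication under the single code PV_MM.503. Section 7.1.3 repeats this, and Section 4, reserved for changes or clarifications to the protocol analyses, declares none.

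Main SAP Section 6 removes subjects from the final PPS for five groups of deviations. They include "Double-blind treatment duration less than 49 days: PV_PP.535", "No or no valid Week 8 SiDBP (hence, no primary endpoint): PV_PP.501 and PV_MM.501" and "Compliance with double-blind treatment < 80% or > 120% or treatment not taken as per protocol". The other two are an antihypertensive still ongoing at randomization (PV_MM.307) and interfering medication under seven codes.

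Re-estimation SAP Section 9 says that the number to randomize is "calculated by dividing PPS size by the proportion of randomized subjects who were included in the PPS", with the lower 95% Clopper-Pearson limit used as the proportion. It adds: "The re-calculated number of subjects randomized is expected to be between 300 subjects and the originally foreseen 540 subjects". Exposure and safety needs are also to be considered. Section 1 anticipates a PPS of at least 80% of the FAS. Main SAP 4.2 reports that the number randomized was lowered to 490.

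**The concern.** The divisor describes a larger set than the one analysed. For the same 100 subjects, nearly every omitted criterion can only take subjects out, so the share seen at the re-estimation tends to exceed the final share. Dividing by too large a share gives too small a number randomized. The lower confidence limit was added because a share from 100 subjects is imprecise. If part of it pays for a known difference in definition, less is left for sampling error. At stake is whether the target of about 90% average power to detect a dose-response holds in the set that carries the primary analysis.

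There is also a smaller point: the expected range of 300 to 540 does not follow from the stated rule and the stated PPS range of 280 to 420.

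**Working it through.** **1. The two definitions**

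| Main SAP Section 6 | In the re-estimation PPS? |
|---|---|
| Treatment under 49 days | No |
| No or no valid Week 8 SiDBP | Yes, in substance |
| Antihypertensive ongoing at randomization | No |
| Interfering medication, 7 codes | 1 of 7 (PV_MM.503) |
| Compliance outside 80–120%, or not taken per protocol | No |

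The 49-day rule partly overlaps with missing Week 8 data. The re-estimation Visit 7 window opens on Day 43, so only subjects stopping at about Days 43–48 with a reading before end of treatment are newly excluded.

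**2. The plan's own inputs reproduce**

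The lower Clopper-Pearson limit for x of 100 is the 2.5% quantile of Beta(x, 101 − x). For 95, 90, 85 and 80 it is 0.887, 0.824, 0.765 and 0.708; Table 3 of the re-estimation SAP gives 0.89, 0.82, 0.76 and 0.71.

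Average power was simulated with the candidate models and four true curves of re-estimation SAP 15.2 (five dose groups, two-sided 0.05). It is 0.904 at SD 8 with 50 per group and 0.903 at SD 9 with 63 per group, in agreement with the 90% rows of Table 2 (PPS 300 and 378).

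**3. The margin in the rule**

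Margin = observed share − lower limit: 6.3, 7.6, 8.5 and 9.2 percentage points at 95, 90, 85 and 80 of 100. Apart from sampling error, the final PPS drops below target only if the omitted exclusions remove more than this.

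**4. Illustration (the extra exclusion rates are assumptions)**

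Take SD 9, target PPS 378 and 90/100 in the re-estimation PPS. Then 378 / 0.824 = 459, or 462 when rounded up to a multiple of six.

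| Further exclusions | Final PPS | Average power |
|---|---|---|
| 5 points | 462 × 0.85 = 393 | 0.91 |
| 10 points | 462 × 0.80 = 370 | 0.90 |
| 15 points | 462 × 0.75 = 346 | 0.88 |

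Had the same exclusions been applied before the limit was taken, the share would be 85 or 80 of 100 for a 5- or 10-point loss. The number randomized would then be 378 / 0.765 = 494 or 378 / 0.708 = 534, against 459.

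**5. The number actually chosen**

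378 / 490 = 0.77 is the final share needed at SD 9, the largest SD tabulated. At SD 8 it is 300 / 490 = 0.61.

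**6. The expected range**

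Number randomized = PPS size / lower limit:

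| In PPS | PPS 280 | PPS 420 |
|---|---|---|
| 95/100 | 316 | 473 |
| 90/100 | 340 | 510 |
| 85/100 | 366 | 549 |
| 80/100 | 395 | 593 |

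A total of 300 needs a lower limit of 280 / 300 = 0.933, or about 98/100, which is above every row of Table 3. A total of 540 needs 420 / 540 = 0.778, or about 86/100. Point estimates do not give the range either: 280 / 0.95 = 295 and 420 / 0.80 = 525.

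**The case against.** A reader might infer that too few subjects were randomized and that the trial is underpowered. The documents do not support that. They give no rate for the omitted exclusions, and a shortfall needs a loss larger than the margin in step 3. The 490 chosen meets the 90% requirement at SD 9 even at the anticipated floor of 80% (490 × 0.80 = 392 against 378).

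Other features lean towards a larger sample. The pooled SD may overstate the within-group SD, by less than 5% according to the re-estimation SAP. The primary model adjusts for baseline, whereas the re-estimation uses the unadjusted SD. There is also a small effect on the share in the opposite direction: main SAP 11.1 accepts office readings up to 5 minutes after end of treatment for Visit 7, while the re-estimation SAP maps readings not before end of treatment to Visit 8. How many subjects the six further medication codes add cannot be judged without the code lists.

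On the range, it is worded as an expectation and exposure and safety needs also enter. It roughly fits the 90%-power sizes: 264 / 0.887 = 298 (SD 7.5, 95/100) and 378 / 0.708 = 534 (SD 9, 80/100).

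All of this limits the consequence. It does not remove the mismatch, which is unacknowledged. It was also partly foreseeable: protocol 5.1.9.2 already treats compliance outside 80–120% as a protocol deviation. And although the range fits the 90% sizes, it is printed beside 280–420, from which it does not follow.

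**Conclusion.** The point holds as a directional bias of unknown size in one input to the sample size. The share is estimated on a PPS with two exclusions and applied to a PPS with five groups of exclusions. The conservative limit is partly spent on that difference. The number randomized may be too low, but only if the omitted criteria cost more than about 6 to 9 points. Under the assumptions of step 4, power is still about 0.90 at 10 points and 0.88 at 15. The outcome of 490 is not shown to be inadequate; that would take a final share below 0.77 at SD 9. The range of 300 to 540 is a wording inconsistency with no demonstrated effect on the 490.

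**What to change.** Apply the full main SAP Section 6 list (duration, compliance, ongoing antihypertensive and all medication codes) to the 100 blinded subjects, and use that set for both the SD and the PPS share. Main SAP 4.2 already reports the outcome, so the practical form now is to report the share under both definitions and note the difference in Section 4 of the re-estimation SAP.

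Restate the expected number randomized from the rule: for PPS 280–420, about 316–473 at 95/100 and 395–593 at 80/100. Alternatively, state that 540 is a cap and give the power if it binds.

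The cost is a deviation and compliance review for 100 subjects and a few corrected numbers. If done prospectively, the re-estimated size might be somewhat larger. In the step 4 example, a 5-point loss adds 494 − 459 = 35 subjects, still inside the original 540.

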7 ANALYSIS SETS

7.1 Definitions of analysis sets

7.1.1 All Randomized Set

The All Randomized Set (RND) includes all subjects with answer ‘YES’ to the question ‘Was the subject randomized?’ in the **Randomization** eCRF.

7.1.2 Full Analysis Set

The FAS includes all subjects in the RND Set, who have a baseline mean trough SiDBP.

7.1.3 Per-Protocol Set

The PPS includes all subjects from the FAS who have a mean trough SiDBP at Week 8 (i.e., time window Visit 7) and did not use forbidden medication deviation as defined in Section 6.

8 DEFINITION OF SUBGROUPS

[figure not shown]
Not applicable.

9 GENERAL STATISTICAL METHODOLOGY

A blinded SSR will be performed by the sponsor after 100 subjects have been randomized and their Week 8 (time window Visit 7) OBPM data are available for analysis. The SSR will consider the overall standard deviation (i.e., based on pooled treatment groups as the SSR is blinded) of the primary endpoint (change from baseline to Week 8 [time window Visit 7] in mean trough SiDBP, measured by OBPM) in the PPS.

The primary endpoint (change from baseline to Week 8 [time window Visit 7] of double-blind treatment period in mean trough SiDBP) will be analyzed using the MCP-Mod approach [Bretz 2005, Pinheiro 2006, EMA 2013]. The blinded SSR will be based on the average power achieved in the MCP-Mod approach, to detect a dose response when the ‘true’ dose-response curve is among the four curves displayed in Figure 1 (copied from protocol figure 2). All four assume that the minimum response will be obtained with placebo (0 mg) and the maximum response (4–5 mmHg, placebo corrected) will be reached at the highest dose of ACT-132577 (50 mg).

Figure 1 Dose response relationships used in power calculations

[figure not shown]

For each of the four dose-response curves the power will be calculated using the `powMCT` function in the R-package `DoseFinding` [Bornkamp 2016]. R-code is included in Appendix 15.1.

The calculation requires an estimate of the standard deviation of the primary endpoint [see Section 10.6] in the PPS. The *average* power is displayed in Figure 2 for primary endpoint SDs ranging from 6–9 mmHg. (For the original sample size calculation 9 mmHg was assumed and > 95% power was required for each of the four scenarios separately.)

Figure 2 Average power to detect dose response

Black SD = 6.0; Red SD = 6.5; Blue SD = 7.0; Green SD = 7.5; Orange SD = 8.0; Purple SD = 8.5; Grey SD = 9.0.

The associated sample sizes (PPS) for 80–95% average power are given in [Table 2](#).

Table 2 Sample size (PPS) needed for 80–95% power to detect a dose-response across various SDs

	SD = 6.0	SD = 6.5	SD = 7.0	SD = 7.5	SD = 8.0	SD = 8.5	SD = 9.0
80% power							
- PPS size	126	150	174	198	222	252	282
- per group*	21	25	29	33	37	42	47
85% power							
- PPS size	144	168	198	222	258	288	318
- per group*	24	28	33	37	43	48	53
90% power							
- PPS size	174	198	234	264	300	336	378
- per group*	29	33	39	44	50	56	63
95% power							
- PPS size	210	252	288	330	372	420	474
- per group*	35	42	48	55	62	70	79

*Expected number. Power based on the MCT test in the MCP-Mod procedure as implemented in the R DoseFinding package, averaged over the four dose-response curves in Figure 2 of this protocol.
 MCP-Mod = Multiple Comparison Procedure - Modeling; MCT = Multiple Contrast Test; PPS = Per-Protocol Set; SD = standard deviation.

Here, SD is the standard deviation of the primary endpoint (independent of treatment assignment, as this is blinded). It is acknowledged that this could be an overestimation of the (unobserved) within group SD, but, given the range of anticipated treatment group differences, this overestimation is likely to be small (< 5%; simulation program in [Appendix 15.2](#)). The re-calculated size of the PPS is expected to be between 280 subjects and the originally foreseen 420 subjects.

The associated number of subjects to be randomized will be calculated by dividing PPS size by the proportion of randomized subjects who were included in the PPS. That proportion will be estimated based on the same 100 randomized subjects considered for the blinded sample size re-estimation. To be conservative, the lower limit of the 95% CI around the proportion will be employed, of which some examples are given in [Table 3](#).

Table 3 **Number and proportion of subjects in PPS and 95% CIs for the proportion at the time of the sample size re-estimation**

Number Randomized	Number in PPS	Proportion in PPS	95% CI*	
100	95	0.95	0.89	0.98
100	90	0.90	0.82	0.95
100	85	0.85	0.76	0.91
100	80	0.80	0.71	0.87

*Clopper-Pearson [[Clopper 1934](#)]

The number of subjects to be randomized will also take into account the need to collect sufficient exposure and safety data and is expected to be between 300 subjects and the originally planned 540 subjects.
CI = confidence interval; PPS = Per-Protocol Set.

The re-calculated number of subjects randomized is expected to be between 300 subjects and the originally foreseen 540 subjects.

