11.5 Sample size

11.5.1 Sample size justification

In a previous study with macitentan in essential hypertension (AC-055-201) the within-group SD for the change from baseline to Week 8 in SiDBP was 7.4 mmHg (90% CI: 7.0–8.0). In the sample size calculations SDs of 7–9 mmHg are considered.

Essential hypertension Protocol AC-080A201 Version 3 30 May 2016, page 91/112

Confidential

It is assumed that the maximum difference versus placebo is achieved at the highest dose of ACT-132577. For the dose-response curves four scenarios were considered [see Figure 2]. These are, in fact, sigmoidal E_{max} curves.

For the sample size it was required that the power to demonstrate the existence of a dose-response relationship is 90% for each of the four scenarios. A total of 70 subjects per group in the PPS (i.e., 420 subjects in total) satisfied this condition and would also allow for sufficiently precise estimation of the dose-response curve. Assuming a drop-out rate of approximately 20%, a total of 90 patients per group would need to be randomized (i.e., 540 in total).

The power for the MCP-Mod approach to demonstrate the existence of a dose-response relationship with 70 subjects per group (PPS) is given in Table 2 for various combinations of placebo-corrected differences and SDs.

Table 2 Power to demonstrate a dose-response relationship with n = 70 per group (PPS)

	Scenario 1	Scenario 2	Scenario 3	Scenario 4
Delta*	4.9	4.5	4.5	4.0
SD				
7	99%	99%	99%	99%
8	99%	99%	99%	99%
9	98%	96%	98%	97%

^{*}Maximum difference versus placebo (mmHg) PPS = Per-Protocol Set

Conservatively assuming that the difference versus placebo is 4 mmHg and the SD is 9 mmHg, the power for the MCP-Mod approach is > 95% for the four scenarios considered.

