11.5.3 Blinded sample size re-estimation

A blinded sample size re-estimation will be performed by the sponsor after 100 subjects have been randomized and their Week 8 BP data are available for analysis (or DB treatment discontinuation before Week 8 is confirmed, where applicable). The sample size recalculation will consider the overall SD of the primary endpoint (change from baseline to Week 8 in mean trough SiDBP, measured by OBPM) in the PPS as well as a more common requirement for the power to detect a dose-response, still allowing for sufficient precision to estimate the dose-response curve [Table 4].

Table 4 Sample size (PPS) needed for 80–95% power to detect a dose-response for various SDs

	SD = 6.0	SD = 6.5	SD = 7.0	SD = 7.5	SD = 8.0	SD = 8.5	SD = 9.0
80% power							
- PPS size	126	150	174	198	222	252	282
- per group*	21	25	29	33	37	42	47
90% power							
- PPS size	174	198	234	264	300	336	378
- per group*	29	33	39	44	50	56	63
95% power							
- PPS size	210	252	288	330	372	420	474
- per group*	35	42	48	55	62	70	79

^{*}Expected number. Power based on the MCT test in the MCP-Mod procedure as implemented in the R *DoseFinding* package, averaged over the four dose-response curves in Figure 2.

Here, SD is the overall standard deviation of the primary endpoint. It is acknowledged that this could be an overestimation of the (unobserved) within group SD, but, given the range of anticipated treatment group differences, this overestimation is likely to be small (< 5%). The recalculated size of the PPS is expected to be between 280 subjects and the originally foreseen 420 subjects.

The number of subjects to be randomized will be calculated by dividing PPS size by the proportion of randomized subjects who were included in the PPS. That proportion will be estimated based on the same 100 randomized subjects considered for the sample size

MCP-Mod = Multiple Comparison procedure - Modeling; MCT = Multiple Contrast Test; PPS = Per-Protocol Set; SD = standard deviation.

Essential hypertension Protocol AC-080A201 Version 3 30 May 2016, page 93/112

Confidential

re-estimation. To be conservative, the lower limit of the 95% CI around the proportion will be employed, of which some examples are given in Table 5.

Table 5 Number and proportion of subjects in PPS and 95% CIs for the proportion at the time of the sample size re-estimation

Number	Number	Proportion	95% CI*	
Randomized	in PPS	in PPS		
100	95	0.95	0.89	0.98
100	90	0.90	0.82	0.95

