## FUNCTIONS

powerMCT <-function (doses, sigma, n, true){

candMod <- Mods(linear = NULL, linlog = NULL, quadratic = -0.5, emax = 0.5,
               sigEmax = c(0.5, 0.5), logistic = c(0.5, 0.5), doses = doses)
contMat <- optContr(candMod, w = rep(n,length(doses)))
trueMod <- Mods(sigEmax = true, doses = doses)

power <- powMCT(contMat = contMat, altModels = trueMod, alpha = 0.05, alternative = "two.sided", n = n, sigma = sigma,
               placAdj = FALSE, df = NA, critV = TRUE, control = mvtnorm.control())

power
}

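### The re-estimation promises about 90% power but sizes on an average over four curves; at the tabled 90% sizes the 4 mmHg scenario has about 83–84%

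*SAP*

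**What the plan says.** **Original requirement.** Protocol 11.5.1 asks that "the power to demonstrate the existence of a dose-response relationship is 90% for each of the four scenarios". The synopsis attaches the 90% to a maximum difference of 4 mmHg and an SD of 9 mmHg, which it calls conservative, and sets the type II error at 0.10.

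**Re-estimation criterion.** Protocol 11.5.3 says the recalculation will consider the overall SD "as well as a more common requirement for the power to detect a dose-response", without naming a level. The footnote to Table 4 says power is "averaged over the four dose-response curves in Figure 2". SSR SAP section 9 says "The blinded SSR will be based on the average power achieved in the MCP-Mod approach", and the footnote to its Table 2 repeats the averaging.

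**Stated objective.** SSR SAP sections 1 and 3 say the size "will guarantee approximately 90% power to detect a dose response relationship", with no mention of an average. Section 4, on changes or clarifications to the protocol, is marked not applicable.

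**A second account of the original rule.** SSR SAP section 9 recalls that for the original calculation "> 95% power was required for each of the four scenarios separately", where protocol 11.5.1 has 90%.

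**The concern.** An average over scenarios guarantees nothing for any one of them. The four curves have different shapes and reach 5, 4.5, 4.5 and 4 mmHg at 50 mg, so a strong first scenario can offset a weak fourth. The fourth is the case the protocol calls conservative, and 4 mmHg is also the difference that SAP 10.6.3 treats as clinically relevant. Someone interpreting a weak or absent dose-response would want the power for that case. Neither sample size table shows it, and the wording of the objective suggests 90%.

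**Working it through.** **Inputs**
- Test: six candidate contrasts (linear, linear in log-dose, quadratic, Emax, sigmoidal Emax, logistic), two-sided alpha 0.05, equal groups at 0, 5, 10, 25 and 50 mg, lisinopril excluded (SSR SAP 15.2). The log-dose offset is 0.5 mg (SAP Table 3).
- True curves (SSR SAP 15.2): ED50/ED90 of 12.5/25, 12.5/50, 25/50 and 25/75 mg, with effects at 50 mg of 5, 4.5, 4.5 and 4 mmHg for scenarios 1 to 4. Protocol Table 2 has 4.9 rather than 5 for scenario 1.
- Sizes: the 90% row of protocol Table 4, which is the same in SSR SAP Table 2.

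**Formulas**
- Hill coefficient h = ln 9 / (ln ED90 − ln ED50), which gives 3.17, 1.58, 3.17 and 2.00.
- Mean effect at dose d is proportional to d^h / (ED50^h + d^h), rescaled to the stated effect at 50 mg. Scenario 4 is then 0, 0.19, 0.69, 2.5 and 4 mmHg.
- With unit-length optimal contrasts c, the non-centrality for each contrast is √n · Σ c_i μ_i / SD. The null hypothesis is rejected when the largest |T| exceeds the multiplicity-adjusted critical value (about 2.17–2.18), with 5n − 5 degrees of freedom. Critical value and power come from 400,000 simulated draws.

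**Reproducing the plan's figures.** Searching for the smallest group size that meets each average-power target gives all 28 cells of SSR SAP Table 2, identical or one per group lower. A one-sided 0.05 test does not match: it puts the average in the 90% row at about 95%.

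**Power by scenario at the tabled 90% sizes**

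| SD | n per group | Sc. 1 | Sc. 2 | Sc. 3 | Sc. 4 | Average |
|---|---|---|---|---|---|---|
| 6.0 | 29 | 97.6% | 89.9% | 92.3% | 83.9% | 90.9% |
| 6.5 | 33 | 97.2% | 89.0% | 91.6% | 82.9% | 90.2% |
| 7.0 | 39 | 97.5% | 89.7% | 92.1% | 83.7% | 90.7% |
| 7.5 | 44 | 97.3% | 89.2% | 91.7% | 83.1% | 90.3% |
| 8.0 | 50 | 97.3% | 89.2% | 91.7% | 83.1% | 90.3% |
| 8.5 | 56 | 97.2% | 89.0% | 91.6% | 82.8% | 90.2% |
| 9.0 | 63 | 97.3% | 89.1% | 91.7% | 83.0% | 90.3% |

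Scenario 4 type II error runs from 100 − 83.9 = 16.1% to 100 − 82.8 = 17.2%.

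**Size at which scenario 4 itself reaches 90%.** This takes 35, 41, 48, 55, 62, 70 and 78 per group for SD 6.0 to 9.0. That is 21–25% above the 90% row and close to the row labelled 95% (35, 42, 48, 55, 62, 70, 79).

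**Effect of the expected minimum.** The documents expect a per-protocol set of at least 280, and 280 / 6 = 46.7, so about 47 per group. Four of the seven 90% sizes (174, 198, 234, 264) lie below 280. At 47 per group, scenario 4 has 96.6%, 93.7%, 89.9% and 85.5% at SD 6.0, 6.5, 7.0 and 7.5. From SD 8.0 the tabled size exceeds 280 and scenario 4 stays at about 83%.

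**The case against.** The strongest reply is that this is an openly declared change of criterion. Both table footnotes state the averaging, SSR SAP section 9 contrasts it with the earlier per-scenario rule, and protocol 11.5.1 governs the original 70 per group, not the re-estimation added later. This stands in part. A reader might infer that the tabled sizes are miscalculated or that the averaging was concealed; neither is so. Disclosing an average does not disclose its minimum, however, and the objective still promises about 90% without qualification.

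A reader might also infer that the trial was run with 83% power at 4 mmHg. The documents do not support that. SAP 4.2 reports 490 randomized. If 80% enter the per-protocol set, the lower bound anticipated in SSR SAP section 1, that is 490 × 0.80 = 392, or about 65 per group. Scenario 4 then has about 95% at SD 7.4 (the SD of the earlier macitentan study), 92% at SD 8, 88% at SD 8.5 and 84% at SD 9. A shortfall would need an SD above roughly 8.2.

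The sizing has conservative features too. If the pooled SD overstates the within-group SD by the full 5% that the SSR SAP allows, scenario 4 rises to about 87%. The primary model also adjusts for baseline, which the power program ignores. With an assumed baseline–change correlation of 0.3 to 0.4 (not in the documents), the two together give about 90–92% at SD 8. Dividing by the lower confidence limit of the per-protocol proportion tends to enlarge the set further. These features soften the practical effect but do not make the stated power that of the tabled sizes.

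**Conclusion.** The point holds as a mislabelled power statement. At the tabled 90% sizes the sponsor's own program gives about 90–91% on average but 83–84% in the 4 mmHg scenario, in all seven SD columns. Type II error there is about 1.6 to 1.7 times the stated 10%. Scenario 2, at 89–90%, is marginally short as well.

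Two limits apply. With a per-protocol set of at least 280, the shortfall is confined to an SD above about 7. And the 83–84% belongs to the scenario 4 shape, not to every curve reaching 4 mmHg: at SD 8 and 50 per group, the four shapes all scaled to 4 mmHg give 81–87%.

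The figures assume the SSR program's contrasts and curves, and a within-group SD equal to the tabled SD.

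A reader who turns to protocol Table 2 for per-scenario power will find 97% for scenario 4 at 70 per group and SD 9, where this program gives about 87%. Protocol Table 4 itself needs 79 per group for 95% average power at that SD. The two protocol tables therefore need reconciling as a separate matter.

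**What to change.** - Restate the objective in SSR SAP sections 1 and 3 as about 90% power averaged over the four curves, and about 83% for the 4 mmHg scenario.
- Add a row with scenario 4 (minimum) power to protocol Table 4 and SSR SAP Table 2.
- Reconcile the original per-scenario requirement (90% in protocol 11.5.1, more than 95% in SSR SAP section 9), and record the move to average power in SSR SAP section 4.

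The cost is one table row and a few sentences, and the stated power becomes less favourable. No change in enrolment is proposed. Sizing on the minimum instead of the average would be a design choice that means enrolling more subjects.
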